## 6.2 LOST TO FOLLOW-UP

A subject will be considered lost to follow-up if he or she fails to attend 2 scheduled visits and is unable to be contacted by the study site staff. A subject will also be lost to follow-up if they fail to complete the 3-month follow-up assessment and cannot be contacted by study staff after documented attempts. Before a subject is deemed lost to follow-up, the research assistant will make at least 3 telephone contact attempts. Contact attempts will be documented in the subject's study file.

# 7 STUDY ASSESSMENTS AND PROCEDURES

## 7.1 STUDY ASSESSMENTS

**Baseline Assessments (completed prior to intervention):** Demographics, intimate partner violence (Abuse Assessment Screen), depression (CES-D-10), anxiety (State-Trait Anxiety Inventory), substance use (Addiction Severity Index-Lite), sexual behaviors, HIV transmission knowledge, PrEP awareness, social support (MOS Social Support Survey), spirituality/religiousness (Ironson-Woods Scale), and trauma screening.

**Post-Intervention Assessments:** Patient satisfaction with intervention (Client Satisfaction Questionnaire CSQ-8) completed immediately following the intervention session.

**3-Month Follow-up Assessments:** Repeat measures of depression, anxiety, substance use, sexual behaviors, HIV knowledge, intimate partner violence, PrEP adherence (if applicable), and stage of change. Qualitative interview exploring study experience and PrEP decision-making.

**Medical Record Data Collection:** PrEP initiation and clinic visit attendance abstracted at 3 months and 12 months post-intervention.

## 7.2 ADVERSE EVENTS AND SERIOUS ADVERSE EVENTS

### 7.2.1 DEFINITION OF ADVERSE EVENTS (AE)

An adverse event is defined as a harmful occurrence to study participants, either study-related or non-study-related. As a result of participation in the PrEP uptake intervention or qualitative interviews, study staff may become aware of an adverse event, including participant distress, suicidal ideation, or disclosure of violence or abuse.

### 7.2.2 DEFINITION OF SERIOUS ADVERSE EVENTS (SAE)

Given the minimal risk of the patient-provider communication intervention, serious adverse events are not anticipated.

### 7.2.3 TIME PERIOD AND FREQUENCY FOR EVENT ASSESSMENT AND FOLLOW-UP

Study staff will assess for adverse events during study visits and interviews. Events will be monitored from informed consent through 7 days after the last study visit.

#### 7.2.4 ADVERSE AND SERIOUS ADVERSE EVENT REPORTING

Because study participation may reflect a unique opportunity to provide referrals for social services and because we are collecting data on depressive symptoms and intimate partner violence, any participant endorsing significant symptoms on either of these measures (or a participant who spontaneously reports these problems) will be provided with a referral for services. Study staff will be trained to make appropriate referrals for clinical care in consultation with the PI and clinic site investigators, including participant distress, suicidal ideation, or disclosure of violence or abuse.

Adverse events will be reported to all relevant IRBs as soon as any study staff member discovers them and consistent with site reporting guidelines, and these will be discussed on weekly calls/in-person meetings between [name] and the research team.

### 7.3 UNANTICIPATED PROBLEMS

#### 7.3.1 DEFINITION OF UNANTICIPATED PROBLEMS (UP)

Unanticipated problems are incidents, experiences, or outcomes that are unexpected, possibly related to study participation, and suggest greater risk than previously known.

#### 7.3.2 UNANTICIPATED PROBLEM REPORTING

Unanticipated problems will be reported to the UAB Institutional Review Board (IRB) within 10 working days of the investigator becoming aware of the problem

## 8 STATISTICAL CONSIDERATIONS

### 8.1 STATISTICAL HYPOTHESES

#### Primary Hypotheses:

- The adapted patient-provider communication intervention will demonstrate feasibility as measured by successful recruitment, enrollment, and retention rates
- The intervention will demonstrate acceptability as measured by patient satisfaction scores
- The intervention will show a preliminary impact on PrEP uptake rates among participants

#### Secondary Hypotheses:

- Participants who initiate PrEP will demonstrate adequate medication adherence and clinic visit adherence

## 8.2 SAMPLE SIZE DETERMINATION

The target sample size of N=125 patient participants provides reasonable precision for estimating feasibility and acceptability measures in this pilot study. For instance, assuming 25% of participants initiate PrEP, the 95% confidence interval width for this proportion would be approximately 15.8%. This sample size is adequate for a pilot study aimed at informing the design of a future larger-scale trial rather than testing definitive efficacy hypotheses.

## 8.3 STATISTICAL ANALYSES

### 8.3.1 GENERAL APPROACH

Quantitative data will be analyzed using SPSS or R. Descriptive statistics will summarize all collected data. As this is a pilot feasibility study, analyses will focus on estimation rather than hypothesis testing, with emphasis on confidence intervals for key parameters.

### 8.3.2 ANALYSIS OF THE PRIMARY EFFICACY ENDPOINT(S)

**Intervention feasibility:** Feasibility will be assessed using descriptive statistics (i.e., counts and proportions) for: recruitment numbers (number of participants screened), enrollment rate (proportion of eligible participants consenting), participant retention (proportion completing 3-month follow-up), PrEP referral acceptance rate (proportion accepting referral among those offered), and intervention delivery completion rate (proportion receiving complete intervention). Reasons for non-participation, referral decline, and incomplete intervention delivery will be summarized using frequency distributions and percentages.

**Intervention acceptability.** Acceptability will be assessed using descriptive statistics (mean and standard deviation) for CSQ-8 scores among patient participants. Missing item responses will be handled according to each instrument's scoring guidelines.

**PrEP uptake changes.** PrEP uptake rates will be compared between the 7-month pre-intervention period and the post-period using binomial logistic regression. Time period (pre-intervention vs. post) will serve as the primary predictor. Uptake proportions (i.e., patients who initiate PrEP over eligible patients referred) and 95% confidence intervals will be calculated to estimate the change in uptake rates between periods.

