## 4 STUDY POPULATION

### 4.1 INCLUSION CRITERIA

Cisgender women; age 18 years or older; HIV-uninfected according to self-report; report any sex with male partners in the past 6 months OR anticipate sexual activity with male partners in the next 6 months; primary language English; willing and able to give informed consent; receiving care at one of the participating clinic study sites.

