### 4.3 STRATEGIES FOR RECRUITMENT AND RETENTION

**Recruitment Methods:** Patient recruitment occurs through three approaches: (1) research assistant pre-screening of electronic medical records to identify potentially eligible patients with upcoming clinic visits; (2) recruitment flyers posted in clinic waiting areas; and (3) direct referral by healthcare providers at participating clinics.

Patients recruited through EMR pre-screening are formally screened during routine clinic visits. Patients recruited via flyers or provider referral either contact the research assistant directly using the phone number on flyers or provide permission to be contacted by study staff for telephone screening.

**Retention Strategies:** Participants receive compensation at each study visit (\$30 baseline, \$30 intervention, \$40 three-month follow-up). Reminder calls are conducted 24 hours before scheduled visits. Flexible scheduling options are provided for follow-up assessments, including in-person or telephone completion.

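### The pre/post uptake contrast has no scheduled pre-period data and no common selection rule, so if the post group is the enrolled cohort, the estimated change mixes any tool effect with recruitment selection

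*Combined protocol and SAP*

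**What the plan says.** The uptake analysis sits among the primary endpoints in Section 8.3.2: "PrEP uptake rates will be compared between the 7-month pre-intervention period and the post-period using binomial logistic regression". The only model term given is period: "Time period (pre-intervention vs. post) will serve as the primary predictor". The uptake proportion is defined as "patients who initiate PrEP over eligible patients referred". The section does not say who the pre-period women are, where their data come from, how many there are, or how being eligible and being referred are established for them.

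Study eligibility (Section 4.1) rests on self-reported HIV status and on willingness to consent. Women must also "report any sex with male partners in the past 6 months OR anticipate sexual activity with male partners in the next 6 months". Recruitment (Section 4.3) starts with pre-screening of electronic medical records (EMR), which finds potentially eligible women who are then formally screened. The list of routes continues: "2) recruitment flyers posted in clinic waiting areas; and (3) direct referral by healthcare providers at participating clinics". Participants are paid $30, $30 and $40 at the three visits.

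For PrEP initiation, Section 7.1 has "PrEP initiation and clinic visit attendance abstracted at 3 months and 12 months post-intervention", and the schedule in Section 1.2 agrees. Nothing in either section covers the 7 months before the intervention.

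**The concern.** Preliminary impact on uptake is part of the primary objective (Section 1.1), and the two-period contrast is the only analysis that addresses it. One side of that contrast has no data collection behind it. The other side, if it is the enrolled cohort, was assembled by steps that no pre-period woman went through: she was not screened by interview, did not consent to a PrEP study, was not paid, did not complete HIV-knowledge and PrEP-awareness measures first, and did not answer a flyer or get put forward by her provider.

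Women who come forward for a PrEP study may be readier to start PrEP whether or not the tool works. A model with period alone would put that difference into the period coefficient. The confidence interval would not reveal it, because it reflects sampling error and not selection. Section 8.2 says the pilot is meant to inform a larger trial, so a distorted change could carry into that trial's planning.

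**Working it through.** **1. The plan's own figure.** Section 8.2 gives "The target sample size of N=125 patient participants" and then, "assuming 25% of participants initiate PrEP, the 95% confidence interval width for this proportion would be approximately 15.8" percentage points. With p = 0.25 and n = 125, the exact (Clopper-Pearson) width is 15.84 points (15.80 with 31 events) and the continuity-corrected Wilson width is 15.80, so the figure reproduces. The Wald width is 2 × 1.96 × √(0.25 × 0.75/125) = 15.2 points, a half-width of 7.6. All of these describe one proportion among all participants. The plan gives no precision for the difference between periods, and no pre-period size or rate from which to derive it.

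**2. Can the two groups be selected alike?**
- Age and attendance at a participating clinic: can be applied from records in both periods.
- Self-reported HIV status, reported or anticipated sex with male partners, willingness to consent: obtained by asking the woman, so not available for women seen before the study.
- Referral: in the study it follows the tool session and goes to interested women (Sections 1.2 and 5.1.1). No pre-period counterpart is defined.

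The outcome source need not differ, since post-intervention initiation is also abstracted from records. The mismatch is in who is counted.

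**3. Illustration of size (all uptake rates and route shares assumed).** Suppose the tool has no effect. Let uptake be 15% in pre-period women and in EMR-identified enrollees, and 40% in flyer or provider-referred enrollees, who make up a share f of the cohort. Post uptake = 15%(1 − f) + 40%f.
- f = 0.2: 12 + 8 = 20%, a spurious rise of 5 points.
- f = 0.4: 9 + 16 = 25%, a rise of 10 points.
- f = 0.6: 6 + 24 = 30%, a rise of 15 points.

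A wider set of assumptions (pre-period uptake 5% to 15%, motivated share 20% to 60%, their uptake two to three times the base) runs from 0.8 × 5 + 0.2 × 10 = 6%, a rise of 1 point, to 0.4 × 15 + 0.6 × 45 = 33%, a rise of 18 points.

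**4. Yardstick.** A spurious difference should be set against the half-width of a difference, 1.96 × √(p1(1 − p1)/n1 + p0(1 − p0)/n0). With an assumed 125 per period:
- 20% vs 15%: 1.96 × √(0.16/125 + 0.1275/125) = 9.4 points.
- 25% vs 15%: 1.96 × √(0.1875/125 + 0.1275/125) = 9.8 points.
- 30% vs 15%: 1.96 × √(0.21/125 + 0.1275/125) = 10.2 points.

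So the illustrated bias runs from about half the half-width to about one and a half times it.

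**5. Limits of the illustration.** It takes uptake over all enrollees, whereas the planned denominator is referred women. Conditioning on referral would absorb some of the motivation effect, and fewer women would make the interval wider. It also gives consent, payment and questionnaires no effect of their own, because EMR-identified enrollees are set equal to pre-period women.

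**The case against.** The strongest reply is that Section 8.3.2 never says that the post group is the enrolled cohort. Its uptake paragraph speaks of patients, while the feasibility and acceptability paragraphs speak of participants. A clinic-wide count in both periods would remove the contrast between records and volunteers. That reading is not excluded, nor is a comparison with the participants' own earlier months. However, neither is described or scheduled, the hypothesis in Section 8.1 concerns uptake among participants, and pre-period abstraction is missing on every reading.

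A second reply is that this is a single-arm pilot that disclaims comparative effectiveness (Section 3.1) and focuses on estimation (Section 8.3.1). That is a good answer to anyone asking for a control arm. It does not remove bias from the estimated change, which is still a primary result.

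Three stronger readings are tempting, and the documents do not support them.
- A reader might infer that pre-period women cannot be selected at all. Records can apply part of the criteria, and Section 4.3 already uses them for pre-screening. Only the full set is out of reach.
- A reader might infer that the plan credits the whole difference to the tool. It hypothesises only a preliminary impact.
- A reader might infer that restricting to EMR-identified enrollees makes the contrast like-for-like. Those women still consented, were paid and completed baseline questionnaires.

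**Conclusion.** The point holds in a limited form. Three facts rest on the text alone: no pre-period data collection is scheduled, the full eligibility set cannot be applied to earlier women, and period is the only predictor named. The confounding by recruitment selection also depends on the post group being the enrolled cohort, which Section 8.1 suggests but Section 8.3.2 does not state. That pre-period data would come from clinic records is likewise an inference, since records are the only stated source for PrEP initiation.

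The size is unknown. The 5 to 15 points are illustrative, and other assumptions give 1 to 18, against a half-width of roughly 9 to 10 points for a difference at an assumed 125 per period. It would go too far to say that the bias must exceed sampling error or must inflate the change. The documents give no route shares or uptake by route, and the referral denominator would absorb part of the effect. The feasibility and acceptability aims are not affected.

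**What to change.** - Add pre-period record abstraction to Sections 1.2 and 7.1.
- In Section 8.3.2, state who makes up each group. Apply the same record-based selection rule and the same denominator in both periods. Keep eligible patients referred as planned, and also show uptake over all record-eligible women, because the tool itself can change who is referred.
- Record each enrollee's recruitment route.
- Add a sensitivity contrast with the post group limited to EMR-identified women, and show flyer and provider-referred women separately.
- State that this removes route selection but not the effects of consent, payment or questionnaires, so the change should not be attributed to the tool alone.

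The cost is protocol wording, one route field in REDCap and some chart review. Part of that review is needed for any pre/post comparison; showing all record-eligible women adds to it. The sensitivity analysis also has a smaller post group. If 75 of 125 women are EMR-identified, the single-proportion half-width at 25% grows from 7.6 points to 1.96 × √(0.25 × 0.75/75) = 9.8 points, and it is wider still among referred women only.

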## 2 INTRODUCTION

### 2.1 STUDY RATIONALE

Cisgender women, particularly women of color living in the rural southeastern United States, remain persistently at risk for HIV infection. Pre-exposure prophylaxis for HIV (PrEP) is a highly effective HIV prevention tool that may overcome barriers experienced by women when using traditional HIV prevention tools, such as condoms, which are primarily used and controlled by male partners. However, we know very little about how to facilitate effective access and use of PrEP for women at high risk for HIV infection. This project seeks to understand how to make PrEP more accessible to these women, which may ultimately affect HIV incidence in this population.

Suboptimal healthcare provider communication about sexual health, HIV/STI risk, and preventive measures like PrEP represents a significant barrier to widespread PrEP uptake. Provider awareness of PrEP for women and willingness to prescribe PrEP to patients is alarmingly low. A collaborative effort among providers and PrEP-eligible women is needed to develop culturally tailored interventions supporting PrEP uptake among women at risk of HIV infection.

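### Section 8.3.2 names only ordinary logistic regression for the pre/post change in PrEP uptake and no interval method for the change; with zero pre-period starts there is no finite odds ratio or two-sided interval

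*Combined protocol and SAP*

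**What the plan says.** The synopsis (section 1.1) lists PrEP uptake among the primary endpoints. Section 8.3.2 states that "PrEP uptake rates will be compared between the 7-month pre-intervention period and the post-period using binomial logistic regression", and adds: "Time period (pre-intervention vs. post) will serve as the primary predictor". No penalised or exact version of the model is named, and no effect measure.

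Uptake is defined as "patients who initiate PrEP over eligible patients referred", so the denominator is the women referred and not all those enrolled. The same sentence says that "95% confidence intervals will be calculated to estimate the change in uptake rates between periods". It does not say whether these intervals are for each period or for the difference, or by what method.

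Section 8.3.1 commits the study to estimation, "with emphasis on confidence intervals for key parameters". The only precision figure is in section 8.2 and concerns one proportion: "assuming 25% of participants initiate PrEP, the 95% confidence interval width for this proportion would be approximately 15.8" percent. Neither the number of women referred in the 7 months before the intervention nor the number who started PrEP is given.

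**The concern.** In a study built on estimation, a primary quantity needs an interval that can be computed whatever the counts turn out to be. Maximum-likelihood logistic regression with one binary predictor reproduces the sample odds ratio of a 2×2 table. If no woman in the pre-period started PrEP, that odds ratio is infinite.

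There is some reason to think that the pre-period could be thin. Section 2.1 says: "Provider awareness of PrEP for women and willingness to prescribe PrEP to patients is alarmingly low". The pre-period is also short, and low provider engagement would tend to reduce the number of women referred.

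If a zero occurs, the effect measure and interval would have to be chosen after the data are seen. If the sentence on intervals were carried out as one interval per period, the reader would still lack an interval for the change. Section 8.2 says the study is to inform a larger trial, and the uptake change with its uncertainty is one of the results that trial would draw on.

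**Working it through.** **Inputs.** From the documents: N = 125 and 25% initiation (section 8.2). The post-period is taken as 31/125 = 24.8%, the nearest whole count. The pre-period counts are assumptions, because the documents give none: 20, 30 or 100 women referred, true uptake of 2 to 10%, and 0 to 3 starts.

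**The plan's own figure.** The exact (Clopper-Pearson) interval for 31/125 is 17.5% to 33.3%, a width of 15.8 points. This reproduces section 8.2, which is not in question here.

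**Chance of zero pre-period starts**, (1 − p)^n:

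| Referred (n) | True uptake (p) | Chance of zero |
|---|---|---|
| 20 | 2% | 0.98^20 = 67% |
| 20 | 5% | 0.95^20 = 36% |
| 30 | 5% | 0.95^30 = 21% |
| 30 | 10% | 0.90^30 = 4% |
| 100 | 5% | 0.95^100 = 0.6% |

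**Odds ratio from the planned model**, OR = (31 × (30 − a)) / (94 × a) for a starts among 30, with log-scale SE = √(1/31 + 1/94 + 1/a + 1/(30 − a)):

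- a = 0: division by zero. The iterative fit diverges and the Wald interval is meaningless. A profile-likelihood interval gives a lower limit of 4.8 and no upper limit.
- a = 1: 899/94 = 9.6, SE = 1.04, 95% CI 1.3 to 73.
- a = 2: 868/188 = 4.6, 95% CI 1.04 to 20.5.
- a = 3: 837/282 = 3.0, 95% CI 0.8 to 10.5.

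**Firth odds ratio.** For a 2×2 table the Firth estimate adds 0.5 to each cell:

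- a = 1: (31.5 × 29.5)/(94.5 × 1.5) = 6.6, against 9.6 by maximum likelihood. The gap indicates the small-sample bias away from 1.
- a = 0: (31.5 × 30.5)/(94.5 × 0.5) = 20.3, with a penalised profile-likelihood interval of 2.7 to about 2,600.

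**Difference in proportions, Newcombe interval.** Let d be the difference, and let l and u be the Wilson limits for each period. The lower limit is d − √((p_post − l_post)² + (u_pre − p_pre)²). The upper limit is d + √((u_post − p_post)² + (p_pre − l_pre)²). The Wilson limits for 31/125 are 18.1% and 33.0%.

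- 0/30 (Wilson 0 to 11.4%): d = 0.248. Lower limit 0.248 − √(0.0674² + 0.1135²) = 0.116; upper limit 0.248 + 0.082 = 0.330.
- 1/30 (Wilson 0.6 to 16.7%): d = 0.215. Lower limit 0.215 − √(0.0674² + 0.1334²) = 0.065; upper limit 0.215 + √(0.0825² + 0.0274²) = 0.302.

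**Separate intervals against an interval for the change.** Take 2/30 before. The separate Wilson intervals are 1.8 to 21.3% and 18.1 to 33.0%, and they overlap. The difference is 18.1 points. Its lower limit is 0.181 − √(0.0674² + 0.1466²) = 0.020, and its upper limit is 0.181 + √(0.0825² + 0.0482²) = 0.277. The overlap suggests no clear change, yet the interval for the change excludes zero.

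**Denominator.** If only 60 women were referred after the intervention (an assumption) and 15 started, 0/30 versus 15/60 gives 25.0 points. With Wilson limits of 15.8 and 37.2% for 15/60, the interval is 0.25 − √(0.0922² + 0.1135²) = 0.104 up to 0.372, wider than with 125.

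**The case against.** The case on the other side is substantial.

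- **Few is not none.** A reader might infer that a handful of pre-period starts also breaks the model. It does not. With one to three starts among 30 the odds ratio and interval exist, and two of the three intervals above exclude 1. Only zero removes the estimate.
- **A zero is not shown to be likely.** Section 2.1 speaks of provider awareness and willingness, not of the rate among women referred. Low willingness may mainly reduce referrals. Section 2.2 reports that women were generally interested in PrEP, especially on a trusted provider's recommendation. With no counts given, the chance of a zero depends entirely on what is assumed.
- **The plan does not say that intervals are per period only.** A reader might take it that way, but the sentence names the change as its target. What is missing is the method.
- **Something usable would remain even at zero.** The uptake proportions are still reported. For 0/30 versus 31/125 the likelihood-ratio statistic is 15.1, and a profile interval has a lower limit. What is lost is a finite estimate and an upper limit.
- **This is a single-arm pilot.** No decision rule rests on the odds ratio.

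All five points stand, and they limit the size of the concern. They do not supply a sparse-count provision or an interval method for a primary endpoint in a plan that puts its weight on intervals.

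**Conclusion.** The point holds as a contingent weakness. The one named model yields no finite odds ratio and no two-sided interval if the pre-period has zero starts, and the interval for the change is left unspecified.

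Under the assumption of 20 to 30 women referred and 2 to 10% true uptake, the chance of a zero is about 4% to 67%. With 100 referred at 5% it is negligible. With one to three starts the problem is imprecision and bias away from 1, not failure. In the zero-start example the difference in proportions is still estimated usefully, at 11.6 to 33.0 points.

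All of this rests on assumed pre-period counts and on 125 women in the post-period denominator. Section 8.3.2 counts only women referred, so the real intervals may be wider.

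**What to change.** In section 8.3.2, state that the change in uptake is the difference in proportions between periods (post minus pre), reported with a Newcombe or Miettinen-Nurminen 95% confidence interval. Say explicitly that the interval is for the difference; the proportion in each period can be shown beside it.

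Keep the odds ratio as supporting information. Fit it by Firth penalised logistic regression with a penalised profile-likelihood interval, or by exact logistic regression, whatever the counts turn out to be. State the expected pre-period denominator if it is known.

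The cost is a few sentences of plan wording and a few lines of R, which section 8.3.1 already allows. No new data are needed. The downside is that the penalised odds ratio is shrunk, and with zero starts its upper limit remains uninformative (about 2,600 for 0/30). That is the reason for the difference in proportions to lead.

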## 3 STUDY DESIGN

### 3.1 OVERALL DESIGN

This is a prospective, mixed-methods pilot demonstration study using a pre-/post-intervention design to assess the feasibility, acceptability, and preliminary impact of a culturally adapted patient-provider communication tool on PrEP uptake among cisgender women receiving care at federally qualified health centers (FQHCs) in Alabama. The study employs an iterative implementation process guided by the Exploration, Preparation, Implementation, and Sustainment (EPIS) framework and Dynamic Adaptation Process (DAP).

Following formative qualitative research with patients and providers (Phase 1), this protocol focuses on Phase 2 implementation activities. Enrollment occurs in iterative cycles with continuous feedback from an Implementation Resource Team (IRT) to refine the intervention throughout the study period. The study uses a single-arm design without randomization, as this is a pilot feasibility study evaluating intervention implementation rather than comparative effectiveness.

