## 5 STUDY INTERVENTION

### 5.1 STUDY INTERVENTION(S) ADMINISTRATION

#### 5.1.1 STUDY INTERVENTION DESCRIPTION

The study intervention consists of a brief patient-provider communication session using a culturally adapted flip-book communication tool, optionally preceded by a 3-minute PrEP informational video. The intervention facilitates structured conversations about HIV risk assessment and PrEP as a prevention option.

During the intervention visit, participants may first watch the informational video about PrEP. The trained study provider then follows up on video content and uses the flip-book communication tool to guide discussion about HIV risk, PrEP candidacy, and prevention options. The session concludes with referral to PrEP services for interested participants or discussion of alternative risk-reduction strategies for those not interested in PrEP.

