#### 9.1.4 DATA HANDLING AND RECORD KEEPING

##### 9.1.4.1 DATA COLLECTION AND MANAGEMENT RESPONSIBILITIES

Data collection is the responsibility of the study staff at the UAB and the partnering clinical sites under the supervision of the Principal Investigator. Informed consent and assessments will be captured via iPad and directly entered into REDCap. All computers or iPads used to collect, store, and manipulate data will be password protected with access to a secure REDCap server provided by UAB Department of Medicine.

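### The pre/post PrEP uptake comparison names no clinic term, so a shift in clinic mix among referred women could bias the within-clinic change in either direction (possible, not shown)

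*Combined protocol and SAP*

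**What the plan says.** Section 8.3.2 sets out a binomial logistic regression of PrEP initiation on period: "Time period (pre-intervention vs. post) will serve as the primary predictor". The uptake proportion is defined there as "patients who initiate PrEP over eligible patients referred". Section 8 names no clinic term, other covariate or stratification for this comparison.

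More than one clinic is involved. Section 3.1 describes women "receiving care at federally qualified health centers (FQHCs) in Alabama", section 4.1 requires "receiving care at one of the participating clinic study sites", section 4.3 lists "direct referral by healthcare providers at participating clinics" as a recruitment route, and section 9.1.4.1 assigns data collection to "study staff at the UAB and the partnering clinical sites". The number of clinics is not stated.

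On design, section 3.1 says "The study uses a single-arm design without randomization", with enrolment in iterative cycles. On who enters the denominator, section 5.1.1 says "The session concludes with referral to PrEP services for interested participants".

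**The concern.** Nothing in the plan holds the clinic composition of the two periods constant. Because the denominator is women referred, and referral follows interest, each clinic's share can move through interest and referral practice as well as through enrolment. If clinics also differ in uptake, part of the crude change reflects which clinics supplied the women.

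PrEP uptake is a primary endpoint, section 8.1 expects the intervention to affect it, and section 8.3.1 makes estimates and confidence intervals the main product. Section 8.2 says the results should inform a larger trial. A mix effect would enter that estimate, and its interval would not show it. Leaving the adjustment unstated also means it could be chosen after outcomes are known.

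**Working it through.** **The plan's own figure.** Section 8.2 gives a 95% interval width of about 15.8% for 25% initiation at N=125. The exact (Clopper-Pearson) interval at 31/125 is 17.5% to 33.3%, width 15.8 points, so the figure reproduces. It concerns a single proportion and says nothing about the comparison of periods.

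**Inputs.** From the documents: period as the only named predictor, initiators over eligible referred women as the outcome, several clinics, N=125 enrolled. Assumed, because the documents give none of them: clinic uptake rates, clinic shares and the number of referred women in each period.

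**Mix shift with no true change.** Let pA and pB be uptake in the higher- and lower-uptake clinic, the same in both periods, and w0 and w1 the higher-uptake clinic's share before and after. Crude uptake is w·pA + (1−w)·pB, so the false change is (pA − pB)(w1 − w0). For example, (0.40 − 0.10)(0.70 − 0.30) = 0.12.

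The 95% half-width of the crude difference is 1.96·SE, with SE = √[p0(1−p0)/n_pre + p1(1−p1)/n_post]. Coverage of the true zero is Φ(1.96−d) − Φ(−1.96−d), with d = false change/SE. Ranges cover both directions of the shift.

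| Clinic uptake | Share w0 to w1 | Crude pre, post | False change (points) | OR (shift reversed) | Coverage, 125 pre/125 post | Coverage, 125 pre/60 post |
|---|---|---|---|---|---|---|
| 20%, 30% | 45% to 55% | 24.5%, 25.5% | 1 | 1.05 (0.95) | 94.6% | 94.8% |
| 20%, 30% | 30% to 70% | 23%, 27% | 4 | 1.24 (0.81) | 88.7% | 90.9–91.0% |
| 10%, 40% | 40% to 60% | 22%, 28% | 6 | 1.38 (0.73) | 80.5% | 85.4–85.9% |
| 15%, 35% | 30% to 70% | 21%, 29% | 8 | 1.54 (0.65) | 68.9% | 77.4–78.7% |
| 10%, 40% | 30% to 70% | 19%, 31% | 12 | 1.92 (0.52) | 40.0% | 55.0–59.0% |

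Last row at 125/125: SE = √[(0.1539 + 0.2139)/125] = 0.0542, d = 0.12/0.0542 = 2.21, coverage 0.400.

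Four clinics at 15%, 20%, 30% and 35%, with shares 40/30/20/10 becoming 10/20/30/40, give 21.5% and 28.5%: 7 points, OR 1.46. If the mix is stable, or the clinics have equal uptake, the false change is zero.

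Half-widths are 10.6 to 10.7 points at 125/125 and 12.8 to 13.6 at 125 pre/60 post. Only the 12-point case exceeds its half-width at 125/125; none does at 125/60.

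**Does adjustment work?** In two-clinic expected counts, with uptake unchanged within each clinic, adding a clinic term to the logistic model returns a period OR of 1.00.

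The Mantel-Haenszel risk difference is Σ w_k(p1k − p0k)/Σ w_k, with w_k = n1k·n0k/(n1k + n0k). Take 15%/35%, 30% to 70%, 125 pre and 60 post. Expected counts are 87.5 and 18 in the low clinic and 37.5 and 42 in the high clinic. The weights are 87.5×18/105.5 = 14.93 and 37.5×42/79.5 = 19.81. The within-clinic differences are zero, so the estimate is zero.

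- Stratified large-sample half-width: 1.96·√[(14.93×0.1275 + 19.81×0.2275)/34.74²] = 14.3 points.
- Crude half-width: 1.96·√[0.1659/125 + 0.2059/60] = 13.5 points. The ratio is 14.3/13.5 = 1.06.

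In simulation (125 pre, 60 or 125 post, two or four clinics, true change zero), the Mantel-Haenszel estimate with Sato variance had bias of about 0 and coverage of 94.4% to 94.9%. In the example above its mean half-width was 14.1 to 14.2 points against 13.4 crude. The crude estimate there averaged about +8 points, with 80% coverage. The smallest expected cell is 18×0.15 = 2.7 initiators, so sparse cells are realistic.

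**Odds ratios.** With equal clinic shares in both periods and a within-clinic OR of 2.00, 15% and 35% become 26.1% and 51.9%. Crude uptake goes from 25% to 39.0%, a crude OR of 1.92. For 10% and 40% the crude OR is 1.81. Crude and adjusted ORs can therefore differ with no mix shift at all.

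**The case against.** The strongest objection is about the target. The section's stated aim is the change in uptake between periods. As a description of that change, the crude difference is not biased by clinic mix, because mix is part of what changed. This stands. The bias exists only if the within-clinic change is wanted, which is the reading closest to the effect on uptake that section 8.1 expects.

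Second, two unseen conditions are needed together, and the large figures require a 30% to 70% reversal of shares that nothing in the documents suggests. This also stands.

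Third, 125 is the number enrolled, and post-period women count only if referred. If they are drawn from enrolled women, 125 is a ceiling. With an assumed 60 pre and 40 post the half-width is about 17 points, larger than any false change above. That reduces the relative importance of mix but does not remove the bias.

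Fourth, calling period the primary predictor leaves room for others. A reader might infer that the plan rules out clinic adjustment; it does not. It names none, and a choice left open can be made after the data are seen.

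Fifth, stratification loses clinics with referred women in only one period. Section 2.1 describes low provider awareness and willingness to prescribe, so clinics with no pre-period referrals are plausible. This is a real cost and should be reported.

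**Conclusion.** The point holds as a minor improvement (CONSIDER). The plan names no clinic term for an unrandomized comparison across several clinics. If the within-clinic change is the target, a change in mix can bias the crude result upward or downward. On the assumed inputs the false change is 1 to 12 points (OR 1.05 to 1.92, or 0.95 to 0.52 reversed). Modest shifts are harmless.

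A reader might infer that the planned estimate is biased. The documents do not support that: they report neither uptake by clinic nor clinic shares in either period. Nor would clinic adjustment turn the result into an intervention effect, since calendar trend and volunteer selection remain in a single-arm pilot.

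**What to change.** In section 8.3.2, state that the within-clinic change is the target and prespecify, before outcomes are seen, one clinic-adjusted comparison. Either of these would do:

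- a clinic term in the planned logistic model; or
- a Mantel-Haenszel risk difference stratified by clinic, with a Sato-variance 95% interval. It suits the section's interest in uptake proportions and tolerates sparse clinic-by-period cells.

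Do not switch between them on observed cell counts. Report the planned crude result alongside, and tabulate initiators and eligible referred women by clinic and period. List any clinic with referred women in only one period: it contributes nothing to the stratified estimate but stays in the crude one. Describe the result as a change between periods. If odds ratios are shown, note that crude and adjusted values can differ through non-collapsibility alone.

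The cost is SAP wording and recording clinic for pre-period women. Their source is not described, so it is an assumption that clinic can be obtained. Intervals are usually slightly wider. A clinic term raises the standard error of the period log OR by about 1% to 14% with two clinics (large-sample figure). The cost with many small clinics was not computed.
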